### 5.1 Screening for Inclusion/Exclusion Criteria & Randomization

Each potential participant's medical record will be reviewed for available inclusion and exclusion criteria data. After the participant provides informed consent, his or her medical history and additional demographic data will be obtained. Initial screening will occur at least 1 day prior to the patient's scheduled ablation procedure.

The pharmacy that prepares the ethanol/placebo infusion bags requires notification of the treatment assignment 1 business day prior to administration in order to prepare the infusion bag. Therefore, participants must be consented and randomized at least 1 day prior to the scheduled procedure.

Baseline measures will include:

- Inclusion/Exclusion criteria assessment
- Demographics and medical history
- World Health Organization AUDIT questionnaire
- CARDIA alcohol use questionnaire (shortened version)
- Vital signs
- Infusion, procedure, BrAC, and EP study measurements
- Arrhythmia episodes pre/during/post-procedure
- Adverse event assessment

### 5.2 Follow-up Visits (Months 3, 6, and 12)

Following an ablation, patients usually return to clinic at 3, 6, and 12 months post-procedure as per standard of care. HOLIDAY safety follow-up data will be collected by chart review. We will collect data on targeted AEs, serious, unexpected AEs, use of antiarrhythmic drugs, use of anticoagulation, incidence and burden of AF or atrial flutter, incidence of ablation or cardioversion, and emergency room visits since the last visit. Participants who do not return to clinic at 3, 6, and 12 months will be contacted by the Study Coordinator to conduct the visit by phone.

Follow-Up Visit measures will include:

- Medication use
- Arrhythmia episodes
- Cardioversions/ablations
- Adverse event assessment

### 5.3 Targeted Concomitant Medications

Current/regular use (since their last study visit) of a specific list of concomitant medications/therapies must be documented at Baseline (pre-study treatment) and at all follow-up visits. Medication data will be collected by chart review and will include type of medication,

frequency, and dosage. The list of targeted medications/therapies includes cardiovascular-related medications (e.g., anticoagulants and antiarrhythmics).

#### **5.4 Targeted Adverse Event (AE) and Serious Unexpected Adverse Event (SAE) Evaluation and Reporting**

An adverse event is any undesirable sign, symptom or medical condition occurring after initiation of the study treatment, even if the event is not considered to be related to study treatment. Medical conditions/diseases present before starting study treatment are only considered AEs if they worsen after starting study treatment (or any procedures specified in the study protocol).

A targeted adverse event (AE) is an event that may be reasonably anticipated to occur as a result of the study procedures or study participation or is part of the normal disease process or progression. Specific targeted AEs are documented in detail in the Operations Manual.

A serious unexpected adverse event (SAE) is defined as being unexpected if the event exceeds the nature, severity or frequency described in the current IRB Application, protocol, and consent form. An unexpected AE also includes any AE that meets any of the following criteria:

- Results in subject withdrawal from study participation, or
- Due to a deviation from the IRB approved study protocol

After completion of the study treatment (at the Baseline Visit) and at all follow-up visits, safety evaluations will include monitoring for targeted adverse events and recording all serious adverse events for the assessment of the secondary exploratory study objective.

Information about targeted adverse events, whether volunteered by the subject, discovered by Principal Investigator questioning, or other means, will be collected and recorded and followed as appropriate.

As possible, each targeted adverse event will be described by:

- duration (start and end dates),
- severity grade (mild, moderate, severe),
- relationship to the study treatment and/or procedure (suspected/not suspected),
- action(s) taken and, as relevant, the outcome.

Even though planned/anticipated pregnancy is a study exclusion, pregnancy during follow-up may occur. If a female study participant should report pregnancy, this should be reported on a Protocol Deviation CRF. The pregnancy should be followed up to determine details of birth, outcome, including spontaneous or voluntary abortion, the presence or absence of any birth defects or congenital abnormalities, or any maternal/newborn hazards.

## **6.0 RISKS AND BENEFITS**

### **6.1 Potential Risks**

The primary risk to participants involves the receipt of IV ethanol. The procedure for IV ethanol infusion is well described and has previously been used for studies in the intoxication literature. The target blood alcohol level of 0.08% that will be achieved is the legal limit for driving in California, and is equivalent to approximately 4 drinks of ethanol in a 180 pound man (equivalent to moderately heavy social drinking in one sitting). The use of IV ethanol in clinical settings is well established, with a long history of use in the treatment of such conditions as

methanol and ethylene glycol poisoning. The blood alcohol levels that have been used in such situations (0.1 to 0.2%) are higher than the level that we will use in our study (0.08%). Side effects from the ethanol infusion at our targeted dose may include mild headache, but it is unlikely to cause nausea and vomiting. Early studies with high dose IV ethanol infusions used for surgical anesthesia in the 1960s targeted to blood ethanol concentrations of 0.2 to 0.4% resulted in dizziness, nausea and/or vomiting. Most of these symptoms resolved by 24 hours. In more recent experiments using the moderate levels of ethanol that we will target (0.08% blood alcohol concentration), only mild headache, with no nausea or vomiting, has been reported. There have been no reports of serious adverse events with IV ethanol titrated by the BrAC quick clamp method. In addition, previous studies in which oral whiskey was administered to patients undergoing invasive electrophysiology (EP) studies (discussed above) did not result in any serious adverse events. While the total volume infused in either the ethanol group or the placebo (D5 half normal saline) group is not expected to exceed 500 cc, there is the theoretical possibility of causing volume overload; of note, patients with a history of heart failure or LVEF < 50% will be excluded. It is possible that ethanol may potentiate the side effects of other sedatives in patients undergoing AF ablation procedures, but this is unlikely. All of these cases are staffed by board certified anesthesiologists (with continuous 12 lead electrocardiograms, pulse oximetry, CO2 monitoring, and blood pressure monitoring per an arterial line per standard of care) as well as a cardiac EP attending, a cardiac EP fellow (board certified or board eligible in cardiology) and two nurses. All patients have several large sheaths in place for venous access, defibrillation pads already in place, and the intracardiac catheters can provide pacing if necessary. An echocardiography machine is immediately available in the EP laboratory and at least one on call interventional cardiologist and interventional cardiology fellow are available in the cardiac catheterization laboratory in the same suite

We observed no complications and no difficulties with recovery or wound healing in the 3 AF ablation patients receiving IV ethanol titrated to a blood ethanol concentration of 0.08% using the BrAC quick clamp method. We are not aware of any evidence to suggest that ethanol should adversely affect the efficacy of the AF ablation or the recovery or wound healing processes.

Additional risks include prolongation of the AF ablation procedure. We anticipate that the additional procedure time will average 40 minutes. The left atrial anatomic map will be created using the three dimensional mapping system per the standard clinical procedure while the ethanol or placebo infusion is started and titrated to steady state, helping to minimize any extra procedure time. This additional procedural time may minimally increase the patient's risk for stroke or sedation complications including pneumonia, deep vein thrombosis, or pulmonary embolism. Although the EP tests that will be performed and attempts to induce AF are consistent with standard of care during AF ablation procedures per the most recent expert consensus (as well as standard of clinical practice in the UCSF cardiac EP laboratory), the potential induction of AF includes a risk of cardioversion, which may minimally increase the risk of skin burns and stroke. As per standard of care, all patients may undergo transesophageal echocardiograms immediately prior to the procedure to exclude the presence of a left atrial appendage thrombus and all will receive IV heparin with serial ACT monitoring to minimize the risk of stroke.

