### 2.6.2 Exclusion Criteria

1. History of substance abuse or alcoholism (determined by history, Alcohol Use Disorders Identification Test (AUDIT) questionnaire, or chart review)

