### 3.4 Infusion

After the first EP study, the intravenous ethanol or placebo infusion will be initiated while the left atrial anatomic map is being constructed to reduce time added to the ablation procedure and minimize risk. The infusion is run by an iMED Gemini PC-2TX pump connected to and controlled by the CAIS 2.0 computer software. The ethanol infusion will consist of a 6% volume/volume ethanol solution in 0.45% saline titrated by the BrAC quick clamp method until a steady state is achieved at a blood alcohol concentration of 0.08%. The mean time to achieving this steady state is regulated by the CAIS 2.0 software to be approximately 20 minutes. Infusion rates are determined by the patient's height, weight, age, and sex, but are automatically adjusted depending on the patient's breath alcohol measurements, which are taken every three to four minutes until steady state is reached.

Patients assigned to the placebo group will receive 5% dextrose (D5) in 0.45% saline. BrAC measurements will be obtained at identical intervals for all participants; BrAC measurements will be randomly generated within two standard deviations of the predicted values calculated by the CAIS 2.0 software based on height, weight, age, and sex. The randomly generated BrAC values will be input into the CAIS 2.0 software, as for patients receiving an alcohol infusion, and the infusion rates will be automatically adjusted accordingly.

Once the BrAC reading is  $\pm 0.002\%$  from 0.080% (steady state), BrAC measurements will be taken every 10 minutes and input into the CAIS 2.0 software. Breath alcohol measurements will be taken using the Intoximeters Alco Sensor IV fitted with a one-way valve adaptor for intubated patients. (See Operations Manual for details)

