### **4.1 Untreated Randomized Participants**

After randomization, if an exclusionary criterion is identified prior to or at the start of the study procedure, the participant will not undergo the study infusion procedure. Randomized participants may be early terminated, prior to commencing the study procedure, and will not receive the study infusion if any of the following study exclusions are identified:

- Participants who present in AF sustained >1 week
- If a participant does not present in sinus rhythm at the procedure, but he or she has proven to be in sinus rhythm at the enrollment visit, it is up to the attending whether or not to cardiovert the patient and proceed with study protocol. If the participant is to be cardioverted, the cardioversion should take place prior to transseptal puncture and following right catheter placement to minimize potential effects on AERP and conduction times. If a second AF episode initiates and is sustained over 2 minutes prior to initiation of study procedure, the study will be aborted.

These participants will be considered as “Untreated Participants”. Unrandomized participants who do not commence/receive the study infusion will not continue in follow-up and will not be included in analyses.

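### Section 6.1 says a history of heart failure is an exclusion, but the exclusion list in Section 2.6.2 has only LVEF below 50%

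*Protocol*

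**What the plan says.** Section 6.1 (Potential Risks) raises volume overload for both arms. The sentence reads in part "group is not expected to exceed 500 cc, there is the theoretical possibility of causing volume overload", and it ends with the reassurance that "patients with a history of heart failure or LVEF < 50% will be excluded". The word joining the two conditions makes a heart failure history sufficient for exclusion, whatever the LVEF.

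Section 2.6.2 lists the exclusion criteria as items 1 to 9. Item 1 is "History of substance abuse or alcoholism" and item 2 is the LVEF limit. The others cover liver tests, clinical liver disease, pregnancy, inability to consent, amiodarone, dofetilide and alcohol intolerance. None names heart failure.

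Two sections put the criteria to use. Section 5.1 says that each candidate's "medical record will be reviewed for available inclusion and exclusion criteria data". Section 4.1 withholds the infusion from a randomized participant "if an exclusionary criterion is identified prior to or at the start of the study procedure".

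**The concern.** Section 6.1 tells its reader that patients at particular risk from added fluid will not be in the study, and it gives two exclusions as the reason. Only one of them is in the list. Staff who screen from Section 2.6.2 could enrol and infuse a patient whom the risk section describes as excluded.

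What is at stake is participant safety and the accuracy of the risk statement. Section 6.2 says participants gain no direct benefit, so a safeguard that the protocol claims should be one that it applies. The fluid load applies to both arms, so the gap does too.

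**Working it through.** The plan gives no figure to reproduce on this point. The check sets the sections side by side.

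**Step 1. Is the list complete as printed?** The numbering in Section 2.6.2 runs from 1 to 9 with no missing item, so lost or blacked-out text does not explain the absence.

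**Step 2. Which patients are treated differently by the two sections?**

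| Heart failure history | LVEF | Section 6.1 | Section 2.6.2 |
|---|---|---|---|
| No | 50% or more | not excluded | not excluded |
| No | below 50% | excluded | excluded |
| Yes | below 50% | excluded | excluded |
| Yes | 50% or more | **excluded** | **not excluded** |

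The sections agree in three of the four cells. They disagree only for a heart failure history with preserved or recovered LVEF.

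**Step 3. Does another section close that cell?**

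- Section 2.6.1 (inclusion) covers age, AF history, the planned procedure and the rhythm at presentation. It does not touch heart failure.
- Section 5.1 (screening) refers to the inclusion and exclusion criteria and does not mention Section 6.1.
- Section 4.1 (before infusion) refers to an exclusionary criterion in general terms. The bullets under it concern AF at presentation, cardioversion and a second AF episode. It does not mention Section 6.1 either.
- Section 8.0 requires the investigator to follow the protocol as a whole but adds no criterion.
- The SAP does not define eligibility.

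Section 6.1 is the only place that makes a heart failure history a ground for exclusion.

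**Step 4. How many patients?** The documents give neither the frequency of heart failure among candidates nor the share with LVEF of 50% or more, so the number cannot be estimated from them.

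**The case against.** The strongest reply is that Section 6.1 is itself part of the protocol, that its statement is categorical, and that Section 8.0 binds the investigator to the whole document. Section 4.1 also bars infusion after a second AF episode, which is not in Section 2.6.2, so that list is not the only place where a bar appears. On this reading a careful investigator would exclude the patient anyway. That is possible, and it is why one cannot say that such patients would in fact be enrolled. But the AF bar stands in the section that staff apply at that moment. The heart failure bar stands in a narrative on risk to which neither screening nor the pre-infusion check points.

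The reply is also right that other protections exist. The LVEF limit is listed. Section 6.1 describes anesthesiology staffing, arterial pressure monitoring, oximetry and echocardiography at hand. Section 7.2.1 has the infusion stopped at once if it is thought to be causing dangerous effects, and Section 4.4 lets the investigator withdraw a participant in the participant's interest. These points stand and reduce the weight of the finding. They do not remove the mismatch.

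A reader might go further and infer that the 500 cc expectation in the same sentence is also wrong. Section 3.4 states that "The ethanol infusion will consist of a 6% volume/volume ethanol solution in 0.45% saline titrated by the BrAC quick clamp method", and Section 6.1 calls the target level "equivalent to approximately 4 drinks of ethanol in a 180 pound man". From the documents alone, 0.06 × 500 = 30 mL of ethanol, and 30 / 4 = 7.5 mL per drink. The protocol gives no drink size, so nothing there contradicts it. A shortfall appears only with outside assumptions:

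- At a density of 0.789 g/mL, 500 cc holds 0.06 × 0.789 × 500 = 23.7 g.
- Four drinks of 8 to 14 g would need 32 / 0.04734 = 676 mL to 56 / 0.04734 = 1,183 mL.
- Taking 0.08% as 0.8 g/L, with full distribution at 0.60 to 0.75 L/kg and no elimination, a man of 180 lb (81.6 kg) would need 0.8 × 81.6 × 0.60 / 0.04734 = 827 mL to 0.8 × 81.6 × 0.75 / 0.04734 = 1,034 mL.
- On those figures 500 cc is still enough for him if distribution is no more than about 48% (500 / 1,034) to 60% (500 / 827) complete. It is also enough at full distribution for a 50 kg patient at 0.55 L/kg: 0.8 × 50 × 0.55 / 0.04734 = 465 mL.

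After the target is reached, "BrAC measurements will be taken every 10 minutes and input into the CAIS 2.0 software", with no stop time in Section 3.4. But that section refers to the Operations Manual, which is not among the documents. The 500 cc is an expectation and not a cap, and no dosing or stopping rule uses it. The documents do not support calling it an error.

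**Conclusion.** The mismatch is real and rests on the text alone, with no outside assumption. It is confined to patients with a heart failure history and LVEF of 50% or more. It should be corrected, but it carries modest weight: the number of patients affected is unknown, the LVEF limit and the procedural monitoring remain in force, and the aims and the arm comparison do not depend on it. The one dependency is on the Operations Manual, which might repeat the heart failure exclusion. Even then, the protocol's own list should agree with its own risk section.

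**What to change.** Add history of heart failure as an item in Section 2.6.2. Sections 5.1 and 4.1 then apply it at screening and before infusion without further change.

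Deleting the words from Section 6.1 would also make the sections agree, and the documents do not show which the sponsor intended. Adding the item is preferable because it keeps a safeguard that the protocol already claims.

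The cost is one line and slightly narrower eligibility. Section 5.1 and Table 2 already collect medical history at screening, so no new assessment is needed.

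As an option, the sponsor may wish to check the 500 cc expectation against the infusion software across the eligible range of body size, age and sex.

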## 6.2 Potential Benefits

There are no direct benefits for participating in this study. However, the knowledge gained from this study may help to elucidate the mechanism underlying AF, which would be pertinent to the ~4 million Americans with the disease. In addition, understanding these particular cardiac

effects may ultimately benefit the greater than hundred million individuals that consume alcohol. This may be particularly important as the media often touts alcohol as being “heart healthy.”

## 7.0 Safety Monitoring

### 7.1 Data and Safety Monitoring Board (DSMB)

HOLIDAY has an independent DSMB that is responsible for safeguarding the interests of study participants, assessing the safety and validity of study procedures, and for monitoring the overall conduct of the study and outcomes data. The DSMB members are independent consultants to the PI at UCSF, and are required to provide recommendations about starting, continuing, and stopping the study. In addition, the DSMB is asked to make recommendations, as appropriate, to the PI about:

- The effects of the HOLIDAY study intervention
- Benefit/risk ratio of procedures and participant burden
- Selection, recruitment, and retention of participants
- Adherence to protocol requirements
- Completeness, quality, and analysis of measurements
- Amendments to the study protocol
- Adequacy of and amendments to consent forms
- Performance of the UCSF centers
- Participant safety
- Notification of and referral for abnormal findings

### 7.2 Safety monitoring for targeted adverse events

#### 7.2.1 Intra procedure monitoring

During the procedure the patient will be monitored by a comprehensive care team. This will include the electrophysiology attending, the electrophysiology fellow (who is a board certified or board eligible cardiologist), the cardiac anesthesiologist attending (who will be unblinded), and 2 electrophysiology lab nurses. They will continually watch the patient for signs of distress, changes on the continual 12 lead electrocardiogram, hemodynamic changes on the arterial line blood pressure, continuous pulse oximetry and heart rate telemetry. If at any time there is a concern that the infusion is causing dangerous effects, it will be stopped immediately. Possible adverse events (AEs) include:

1. Hypotension: If hypotension occurs during the ethanol administration, intravenous fluids and presser medications will be administered as appropriate by the cardiac anesthesiologist. The anesthesiologist will have the prerogative to stop the infusion if he/she feels that the infusion is contributing to the hypotension and if it is not controlled with fluids or pressers.
2. Hypertension: If hypertension beyond a systolic blood pressure of 180 mmHg occurs during the ethanol administration, the cardiac anesthesiologist may administer intravenous blood pressure medications such as metoprolol, hydralazine, or nitroglycerin. The anesthesiologist will have the prerogative to stop the infusion if he/she feels that the infusion is contributing to the hypertension and if it is not controlled with blood pressure medications.
3. Atrial Fibrillation: This is to be expected and will be dealt with as appropriate. This may include electrical cardioversion or observation depending on what phase of the procedure the patient is in. It is important to emphasize that some of these procedures

are routinely performed while a patient is in atrial fibrillation for several hours or throughout the entire case.

4. Pulmonary compromise: The patients will be monitored by the anesthesia team throughout the procedure and the level of ethanol that we will target is not associated with respiratory depression. There is no evidence that ethanol (particularly at modest doses) affects oxygenation. The ethanol infusion can be stopped and the patient can be intubated if there are signs of pulmonary compromise.
5. Agitation: The patient will be monitored by the anesthesia team and agitation induced by ethanol will be dealt with appropriately with sedatives.

The PI will also monitor for AEs in all study participants. The research team will discuss the progress of the study and all AEs at weekly research and MMM conferences. At those meetings, feedback will be obtained from attendees. These meetings will also include the Chief of Cardiology, Chief of the EP service, head of quality assurance for electrophysiology, nurses, other EP faculty, fellows, and staff.

